Statistical analysis:	
Safety population: All participants who received study treatment at least once will be included in the safety population. This is the primary population for safety and tolerability analysis.
 
Intention-to-Treat (ITT) population: The ITT population will consist of all

participants as they are randomized to the study. Primary and secondary ophthalmic endpoints will be analyzed by ITT population. In this non-inferiority setting, analysis based on ITT population provides supportive evidence to analyses based on Per Protocol population.

Per Protocol (PP) population: All participants who received at least 25% of the total planned dose for IMP, had at least one valid baseline and post baseline evaluation by SD-OCT and qFAF, and had no major protocol deviations will be included in the PP population. This is the primary population for the primary safety endpoint analysis and other secondary ophthalmic endpoints.

Though this is a safety study, all subjects will be analyzed in the treatment group to which they were randomized. Detailed aspects of the analysis will be presented in the statistical analysis plan (SAP), which will be finalized prior to breaking of the study blind and database lock.

In general, for safety analyses, descriptive statistics will be tabulated by treatment group for all participants. Unless otherwise stated, all safety analyses will use the Safety population. The analysis of AEs will consider only AEs occurring for the first time, or worsening, during or after the first administration of study medication. The analysis will focus on incidence of AEs in the treatment groups, although for AEs of special interest, the number of events will also be provided (i.e. ophthalmic assessments). Tables summarizing AEs will be displayed by preferred term and system organ class (SOC). Analysis of Serious Adverse Events (SAEs) and the categorization of AEs by severity and relationship to study medication will also be included. AEs leading to study withdrawal or deaths on-study will also be presented in tables and/or listings.

Treatment-emergent changes in vital signs and laboratory parameters will be presented using tabulations by group. Descriptive statistics for each parameter and/or the change from baseline at each time point will be provided. For endpoints measured on a categorical scale the number of participants and percentages will be provided.

Primary Endpoint Measures

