5. STUDY DESIGN

5.1. Overview

This randomized, double-blind, placebo controlled study will involve 600 healthy (G6PD normal) volunteers and will run in three parts. The Study Site may stagger enrollment of participants into weekly groups to accommodate the screening period.

Part 1 – Treatment phase (52 weeks)

Participants who meet the eligibility criteria will be randomized (ratio 1:1) using clinical site as a randomization variable to receive a loading dose of either tafenoquine 200 mg (2 x 100 mg tablets) or placebo daily for 3 consecutive days starting at Day 1, Week 1 (Visit 2), followed by study treatment (tafenoquine 200 mg or placebo) once per week for 51 weeks with safety follow-up visits at Weeks 4, 12, 24 and 52 (Visits 3, 4, 5, and 6). All efforts will be made to retain participants through to study completion. The reasons for withdrawal may include: 1) withdrawal of consent, 2) lost to follow-up, 3) evidence of substance abuse that may affect the participant's capacity to complete the study in the investigator's opinion, and 4) development of a new or worsening psychiatric disease (including suicidal ideation) at a non-scheduled visit or during routine M.I.N.I. evaluation that would jeopardize the safety of the participant if they continued in the study (see [Section 9.2.7](#)). If a participant stops taking their study drug, they should continue to have all follow-up safety visits. If the subject wants to withdraw, they should have an EOS visit (preferably 65-75 days after cessation of study treatment that includes all of the Week 64 assessments). The reasons for any treatment discontinuation (temporarily or permanently) will be documented on the eCRF.

Part 2 – Follow-up phase (12 weeks)

Due to the long t_{1/2} of tafenoquine (13-15 days with an expected 65-75-day washout period), all participants will return to the clinic at the Week 64 (Visit 7a and 7b) for their EOS visit. If the participant has an ongoing AE, they will continue in Part 3 of the study, otherwise this is the final visit.

Part 3 – Follow-up Phase (every 12 weeks, up to 12 months)

Participants who meet the criteria for continuation for additional safety assessments at Week 64 (Visit 7a and 7b) will continue to be assessed for up to 3 more times at approximately 12-week intervals or until resolution or stabilization of the AE whichever is earlier.

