5.6. Route of Administration, Dosage Regimen, Treatment Period, and Justification

The 600 study participants will be randomized to the tafenoquine or the placebo group in a 1:1 ratio using clinical site as a randomization variable; two groups of 300 participants each will be enrolled in each group.

Each active IMP tablet will contain 100 mg tafenoquine. The dose to be administered orally is 200 mg tafenoquine (2 x 100 mg tablets) per day for three consecutive days (loading doses), followed by another 200 mg dose once per week for the following 51 weeks (beginning post-loading dose Day 10). The placebo group will receive identically-matched double-blind placebo tablets. The IMP tablets will be taken with 180 mL of water but there is no restriction on whether the tablets are taken with or without food.

Safety evaluations will include the following assessments: AE evaluation, physical examination, vital signs, laboratory parameters (hematology, biochemistry, and urinalysis). These will be performed at various time points throughout the study to assess baseline function and any changes from baseline after administration of IMP. Hematology, including methemoglobin assessment, biochemistry and urinalysis will be conducted at Screening, Weeks 4, 12, 24, 52, and 64. Clinical laboratory values indicative of an AE at EOS Week 64 will be repeated during the Follow-up Phase at Weeks 76, 89, 104 until resolution or stabilization.

Previous clinical studies support a recommended dosage tafenoquine regimen for malaria prophylaxis of a loading dose of 200 mg once daily for 3 days before travel to a malarious area, followed by weekly 200 mg maintenance doses while in the malarious area, for a period not exceeding 6 months, and an additional dose of 200 mg at one week of return from travel (60P IB).

In this study tafenoquine will be administered for 12 months to confirm the long term safety of tafenoquine past the 6-month safety window for travelers or military personnel who may be in a malarious area for prolonged periods of time.

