7.2. Packaging, Labeling and Storage

7.2.1. IMP – Tafenoquine and Placebo Tablets

Tafenoquine/placebo tablets are manufactured by Piramal Enterprises Limited, [name], (Formerly Piramal Healthcare Limited) Pithampur, 454775, India. Tafenoquine and placebo tablets are packed into child-resistant aluminum/aluminum blister packs with 8 tablets per pack.

Investigational products will be provided in drug kits containing 14 blister packs of either tafenoquine tablets or identically matched placebo tablets in each kit. Within each kit, blister packs will be sub-packed into boxes containing, 3, 4, or 7 blisters packs to provide participants with sufficient IMP between dispensing visits, plus enough extra tablets for the study windows, so there should be no interruptions in dosing. Packaging and shipment of clinical supplies to the site will be performed by Catalent, Inc., Philadelphia, USA. Each kit will contain a total of 112 tablets, thus providing a sufficient supply of tablets for the entire study for a single participant in one kit plus 4 extra tablets. The content of the labeling will be in accordance with the TGA GMP requirements (Annex 13 of [PIC/S 2009](#)) and the label will include information regarding the identity (blinded), lot number, expiry date and storage conditions (both tafenoquine and placebo to maintain the blind). Drug kits used in the United States will have additional labeling in accordance with FDA requirements (i.e., “Caution: New Drug – Limited by Federal Law to Investigational Use”). Kits will have a sequential numeric code to blind the identity of the IMP and will be randomly assigned to participants by kit number.

Tafenoquine is marginally light sensitive. Tafenoquine can be transported and stored at ambient room temperature (i.e., between ≥ 15 and $\leq 25^{\circ}\text{C}$), protected from light, in a secure

location accessible to authorized personnel only. Storage conditions must be adequately monitored and appropriate temperature logs maintained throughout the study while IMP is stored at site. Temperature excursions are permitted to 15°C to 30°C (59°F to 86°F). Participants will be instructed to store their IMP in a cool, dry place out of reach of children. The aluminum/aluminum blister packaging protects the IMP from light.

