8.2. IMP Loading Dose: Starting Day 1 of Week 1 (Visit 2)

Participants will report to the Study Site on the morning of Day 1. After completion of the pre-dose assessments, they will receive a single dose of tafenoquine or placebo with water and their first participant drug pack will be issued. Participants will be advised to take doses 2 and 3 in Week 1 at home. The following week, the participant will need to take their dose (2 x 100 mg tablets) commencing 7 days after their last loading dose on Day 3 of Week 1 and continue weekly (every 7 days), thereafter.

The following information will be obtained prior to randomization to collect baseline data and confirm continued eligibility:

- Confirmation of consent/signed informed consent.
- Update information regarding any new medical conditions, medicines (including herbal products and nutritional supplements), surgery or illnesses since screening.
- Update information on social history since screening.
- C-SSRS interview.
- Abbreviated physical examination (pre-dose). A symptom-directed physical examination may also be performed if it is required according to the opinion of the investigator.
- Vital signs (blood pressure, pulse rate, respiratory rate and sublingual body temperature) after resting in a seated position for 5 minutes (pre-dose).
- Blood sampling for determination of the following parameters:
 - CBC, MetHb% and biochemistry; and
 - PK blood sample for tafenoquine.
- Alcohol breath test.
- Urine sampling for determination of the following parameters:
 - Urine pregnancy test (β -HCG) (pre-dose, WOCBP participants only);
 - Urinalysis (dipstick and urine microscopy if blood, leukocyte esterase, or nitrites are positive);
 - Urine drug screen (amphetamines, methamphetamines, barbiturates, benzodiazepines, cocaine, methadone, opiates, phencyclidine, tetrahydrocannabinols, and tricyclic antidepressants); and
- DHI assessment (only collected in participant reports AE of dizziness or vertigo).
- LSEQ assessment.
- Inclusion/exclusion criteria confirmed.

The following will be performed after continued eligibility is confirmed:

- Randomization number obtained by IWRS;
- IMP administration (2 tablets with water).
- Dispense investigational product and provide instructions on use of diary card and text messaging reminder and compliance system.

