Intention-to-Treat (ITT) population: The ITT population will consist of all participants as they are randomized to the study. Primary and secondary ophthalmic endpoints will be analyzed by ITT population. In this non-inferiority setting, analysis based on ITT population provides supportive evidence to analyses based on Per Protocol population.

Per Protocol (PP) population: All participants who received at least 25% of the total planned dose for IMP, had at least one valid baseline and post baseline evaluations by SD-OCT and qFAF, and had no major protocol deviations will be included in the PP population. This is the primary population for the primary safety endpoint analysis and other secondary ophthalmic endpoints.

Though this is a safety study, all subjects will be analyzed as randomized in all the above study populations.

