12.2.3.1. Primary Endpoint

The primary endpoint is the proportion of participants with protocol-defined SOSE. SOSE is assessed by significant retinal changes from baseline using SD-OCT and qFAF. The details of significant protocol defined retinal changes using SD-OCT and qFAF are defined [Table 5](#).

A detailed list of SD-OCT and qFAF parameters assessed in this study is presented in [Appendix 1](#) and [Appendix 2](#). Clinically significant changes for quantitative measures will be defined as a change from baseline by a threshold taken from previously published coefficient of repeatability ([Table 5](#)). For qualitative assessments, new findings or worsening of findings from baseline exams regarded to be of clinical importance by the Blinded Reading Site will be considered a change from baseline. If either of the automated reading (CST or TMV) is missing or deemed unreliable by the Blinded Reading Site; the parafoveal (inner ring of the ETDRS grid; the annular zone between foveal centered 1 mm diameter circle and 3 mm diameter circle) retinal thickness will be used to impute the missing data.

A descriptive summary table will be produced showing the results by each eye and across both eyes, for each assessment (including follow-up). The actual SD-OCT image of each eye will be included in the eCRF. Data from repeated tests carried out due to abnormal values will not be tabulated. All data, including those from repeat tests, will be provided in a listing.

For this primary endpoint, a participant will be considered to have a clinically significant SOSE if any of the five parameters listed below indicates a change from baseline in either eye at any time point during treatment. The 95% CI of SOSE rate will be calculated by treatment group, using the Clopper Pearson Exact methodology for the proportion of participants who did experience a clinically significant deterioration. The risk difference of the SOSE rates between tafenoquine and placebo will be estimated. The upper limit of two-sided 95% CI for the risk difference will be compared against the protocol pre-specified NI margin.

Table 5: Primary Endpoint Evaluation Criteria

Parameter	Result (change from baseline)	Criteria for Clinically Significant Change from Baseline ^a
SD-OCT CST ^b	Yes/No	Yes = change from baseline of at least 40 μm (15% change)
SD-OCT TMV ^c	Yes/No	Yes = change of $\geq 10\%$ (0.86 mm^3) from baseline

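### Non-inferiority on the primary safety endpoint is decided in a Per Protocol set that can omit participants with an observed SOSE, and no rule applies if ITT disagrees

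*Combined protocol and SAP*

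**What the plan says.** Section 12.1 (Analysis Sets) and the Synopsis (Statistical analysis) define the Per Protocol set by three joint conditions. Participants must have "received at least 25% of the total planned dose for IMP, had at least one valid baseline and post baseline evaluations by SD-OCT and qFAF". They must also be free of major protocol deviations. Of this set the plan says: "This is the primary population for the primary safety endpoint analysis and other secondary ophthalmic endpoints". The ITT set holds everyone randomised, and the ophthalmic endpoints are also analysed in it, but "analysis based on ITT population provides supportive evidence to analyses based on Per Protocol population".

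Under Section 12.2.3.1 a participant has a SOSE "if any of the five parameters listed below indicates a change from baseline in either eye". Table 5 lists four SD-OCT parameters and one qFAF parameter, so either modality alone can make an event. The Per Protocol definition makes no exception for a participant in whom a SOSE has been seen.

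Section 5.1 keeps people who stop drug under observation: "If a participant stops taking their study drug, they should continue to have all follow-up safety visits".

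The time frame of the event is worded in two ways. Section 12.2.3.1 counts changes during treatment. The sample size part of the Synopsis counts changes at any follow-up visit.

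**The concern.** Entry to the primary set is stricter than the definition of the event counted in it. Two kinds of participant with a recorded SOSE fall outside it: those who stop drug early, and those with an event in one modality but no valid baseline or post-baseline evaluation in the other.

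In an efficacy non-inferiority trial, a Per Protocol primary analysis guards against non-adherence diluting a real difference. Here the endpoint is harm, and stopping drug may itself follow from the harm. Leaving such events out can shrink the difference under test. With so few events expected, one or two omissions could decide whether non-inferiority is declared.

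**Working it through.** **1. The plan's own figures.** Inputs from Section 12.1: 300 per arm, 1% SOSE in each arm, margin 2.5 points, one-sided alpha 0.025.
- Power = Φ(0.025 / √(2 × 0.01 × 0.99 / 300) − 1.96) = 86.8%, against 86% stated.
- P(at least one event in 300 at 1%) = 1 − 0.99^300 = 95.1%, against 95% stated.
- Expected events per arm = 300 × 0.01 = 3.

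The sample size is not in question.

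**2. The dose threshold.** Section 5.6 plans 3 loading and 51 weekly doses, which is 54 doses or 108 tablets. Section 7.2.1 agrees: "Each kit will contain a total of 112 tablets, thus providing a sufficient supply of tablets for the entire study" for one participant, with 4 spare, and 112 − 4 = 108.
- 25% of 54 = 13.5 doses. 13/54 = 24.1% is out; 14/54 = 25.9% is in. In tablets the cut is 27, or 13 full doses plus one tablet.
- Section 8.2 has weekly dosing "commencing 7 days after their last loading dose on Day 3 of Week 1 and continue weekly (every 7 days), thereafter". Weekly doses fall on Days 10, 17, 24 and so on, and dose 14 on Day 10 + 7 × 10 = Day 80.
- The first post-baseline scan is at Week 12 ± 2 weeks (Sections 8.6 and 9.2.6), so from about Day 64. A fully adherent participant has taken 11 doses (20.4%) by Day 64 and 13 (24.1%) by Day 79.

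Someone scanned between about Day 64 and Day 79 who shows a Table 5 change and takes no dose after Day 79 at the latest is therefore outside the Per Protocol set.

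**3. The imaging threshold.** Entry needs a valid baseline and at least one valid post-baseline evaluation in both modalities; a SOSE needs one modality. Section 12.2.3.1 gives a substitute for a missing or unreliable CST or TMV, but none for qFAF.

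**4. Effect of one omitted event.** The plan does not name the interval for the risk difference, so two are shown.
- Wald: U = d + 1.96 √(p₁(1−p₁)/n₁ + p₀(1−p₀)/n₀).
- Newcombe: U = d + √((u₁−p₁)² + (p₀−l₀)²), where u₁ and l₀ are Wilson limits.

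Wald for 5/300 vs 3/300: d = 0.667%, SE = 0.936%, U = 0.667 + 1.835 = 2.501%. For 4/299 vs 3/300: d = 0.338%, SE = 0.878%, U = 2.06%.

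| Tafenoquine vs placebo 3/300 | Wald upper limit | Newcombe upper limit |
|---|---|---|
| 5/300 | 2.501%, fails | 2.94%, fails |
| 4/299 (one omitted) | 2.06%, passes | 2.49%, passes |
| 6/300 | 2.94%, fails | 3.39%, fails |
| 4/298 (two omitted) | 2.07%, passes | 2.503%, fails |

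One event moves the difference by about 1/300 = 0.33 points, or 13% of the margin.

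**5. Effect on false non-inferiority.** The true rates are set on the margin: 1% placebo and 1% + 2.5% = 3.5% tafenoquine, 300 per arm. Each tafenoquine event is omitted with probability f, and its carrier leaves the denominator too. The probabilities are exact binomial sums. The documents give no value for f, so a range is assumed.

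| f (assumed) | Wald | Newcombe |
|---|---|---|
| 0 | 4.1% | 2.1% |
| 2% | 4.6% | 2.4% |
| 5% | 5.4% | 2.8% |
| 10% | 7.1% | 3.8% |
| 20% | 11.9% | 6.6% |

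**The case against.** Several points on the other side stand.

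- **The ITT analysis is already planned**, and all data, including repeat tests, are listed. A reader might infer that the events are deleted, or that ITT cannot overturn the Per Protocol result. The documents say neither. They call ITT supportive and are silent on disagreement; that silence is the gap.
- **The dose route is narrow.** If only changes during treatment count, a fully adherent participant's event at a scheduled scan is lost this way only when the scan falls between about Day 64 and Day 79 and drug stops before dose 14. Events at Weeks 24 and 52 in adherent participants are safe. Missed doses and unscheduled scans widen the route, as does the Synopsis wording of any follow-up visit. Sections 5.1 and 5.4 list no ophthalmic reason for withdrawal.
- **The imaging route is narrow.** One valid post-baseline evaluation per modality is enough, both modalities are scheduled at Weeks 12, 24, 52 and 64, qFAF is a set of three images, and exclusions 3b and 6 screen out people who cannot be imaged or examined adequately.
- **Loss by arm is not documented.** A reader might infer that early stopping or poor images will be commoner on tafenoquine. No passage supports that. Table 1 shows discontinuation for visual complaints in one tafenoquine and one placebo participant, so such stopping happens, but this gives no direction. Balanced loss would still shrink an absolute difference: with 10% of events lost in both arms, 3.15% − 0.90% = 2.25 points instead of 2.5, ignoring the small change in denominators.
- **The 5-versus-3 Wald case sits almost on the margin.** It shows how sensitive the decision is, not how often it would change.

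**Conclusion.** The concern holds in limited form. As written, non-inferiority on a harm endpoint is decided in a set that can omit observed events, while the set that keeps them has no stated part in the decision. The threshold of 14 doses, Day 80, follows from the documents, as does the mismatch between needing both modalities for entry and one for an event.

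The size rests on assumptions. Bias towards non-inferiority from unequal loss requires omitted events to fall more on tafenoquine. The share omitted is unknown and, given how narrow the routes are, may lie at the low end of the range: at 2% to 5%, false non-inferiority rises by 0.5 to 1.3 points (Wald) or 0.3 to 0.7 points (Newcombe). At 20% it roughly triples. The documents do not support a claim that the primary analysis will be biased, only that it is open to a bias the plan could close with data it already collects.

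**What to change.** In Sections 12.1 and 12.2.3.1 and in the Synopsis, state that non-inferiority is concluded only if the upper limit of the two-sided 95% CI for the risk difference is below 2.5% in both of these sets:

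1. the Per Protocol set as now defined;
2. all dosed participants, as randomised, with a baseline and at least one post-baseline scan, counting any observed SOSE whatever fraction of the dose was taken and whether or not the other modality is valid.

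Keep the requirement for both SD-OCT and qFAF in the Per Protocol definition. Relaxing it to either modality may look simpler, but a participant with a clean SD-OCT and no valid qFAF would then count as event-free with one of the five components never assessed. The second set does carry that weakness, which is why it should stand beside the Per Protocol set and not replace it. The two wordings of the SOSE time frame should be reconciled in the same edit, since they determine how wide the dose route is.

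The cost is a wording change and one run of the same analysis, close to the ITT run already planned. The chance of success falls somewhat because both sets must meet the margin. The documents give no dropout or exclusion rates from which to calculate by how much.
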